5 ANALYSIS SETS

The following analysis sets will be defined for the statistical analysis of this clinical study:

Randomized Set (RS)

The randomized set is defined as all subjects randomized into the study.

Safety Evaluation Set (SES)

The Safety Evaluation Set (SES) is defined as all subjects who receive an investigational product.

Full Analysis Set (FAS)

The Full Analysis Set (FAS) is defined as all subjects randomized and who receive an investigational product with at least one post-baseline effectiveness assessment (i.e. WSRS, blind evaluator's GAIS or subject's GAIS assessment).

Per Protocol Set (PPS)

The Per Protocol Set (PPS) is defined as the subset of the FAS without any major protocol deviations. Major protocol deviations will be finalized during the Blind Data Review Meeting (BDRM) prior to database lock.

6 VARIABLES FOR ANALYSIS

[figure not shown]
6.1 Effectiveness Variables

6.1.1 Primary Effectiveness Variable

The primary effectiveness variable is the treatment success at Month 6. Treatment success is defined as a ≥ 1 -point improvement in NLF from baseline as assessed by a blinded evaluator on a 5-point Wrinkle Severity Rating Scale (WSRS).

6.1.2 Secondary Effectiveness Variable

The secondary effectiveness variable is the “improvement” in the blinded evaluator’s Global Aesthetic Improvement Scale (GAIS) score for the NLF at Month 6. An “improvement” on the GAIS will be classified as “improved”, “much improved”, or “very much improved”.

6.2 Safety Variables

Adverse events (AEs) including serious adverse events (SAEs), AEs related to treatment as assessed by the investigator, and AEs leading to discontinuation during the study. Other safety variables include vital signs and clinical laboratory assessments.

6.3 Other Variables

Other variables include

- Demographics
- Medical History
- Concomitant Medications/Treatments

7 STATISTICAL ANALYSIS METHODS

The effectiveness analyses on the WSRS and Blinded evaluator's GAIS will be carried out on the PPS and for sensitivity of their analyses on the FAS. All safety analyses will use the SES.

In the efficacy tables, mean and standard deviations will be reported with two decimal places. In all other tables, mean, standard deviation, and median will be reported to one decimal place greater than the data were collected; for derived data an adequate number of decimals has to be chosen. Percentages will be calculated using the denominator of all subjects in a specified population or exposed to a specific treatment. The denominator will be specified in a footnote to the tables for clarification if necessary. Percentages will be reported to one decimal place.

7.1 Effectiveness Endpoints

For categorical variables, frequencies of raw values and (where applicable) frequencies of changes from baseline will be shown by treatment and visit together with means and standard deviations.

Response variables are shown by visit as number and percentage of subjects with response (=proportion) at that visit per treatment together with the difference of the (paired) treatment response proportions and its corresponding 95% confidence interval computed according to Newcombe's recommended method¹ [Newcombe, 1998, method 10]. In addition, cross tables are provided showing number (and percent) of subjects with response/non-response on the Radiesse treated side vs. response/non-response on the Restylane treated side by visit.

For WSRS raw values and changes from baseline as well as for blinded evaluator's GAIS, cross tables are prepared showing frequencies of values observed on the Radiesse treated side vs. values observed on the Restylane treated side by visit.

7.1.1 Primary Effectiveness Endpoint

The primary effectiveness endpoint is the difference in proportions of responding NLF sides (NLF sides with treatment success) in the Radiesse and Restylane groups at Month 6. The difference in proportions (D) is defined as the difference between the proportion of responders on the side treated with Radiesse (P_{test}) and the proportion of responders on the side treated with Restylane (P_{control}), i.e.:

$$D = P_{\text{test}} - P_{\text{control}}$$

As a result thereof, the null and the alternative hypothesis notations will be as follows:

$$H_0 : D \leq -\Delta \text{ (null) versus } H_1 : D > -\Delta \text{ (alternative)}$$

To test the non-inferiority of test in comparison to control, a two-sided 95% confidence interval (CI) will be constructed around D. The non-inferiority margin Δ , the clinically negligible difference, is 0.10 (or 10.0%). H_0 will be rejected if the lower bound of the 2-sided 95% CI lies above the non-inferiority margin of $-\Delta$ (-10%), i.e. a conclusion of non-inferiority of Radiesse to Restylane. The two-sided 95% CI for the differences between proportions (paired) will be constructed using the Newcombe's recommended method¹ [Newcombe, 1998, method 10]. The SAS code is provided as below:

First, obtain the Wilson score confidence intervals for the responding proportions in two groups, denoted as l_2 , u_2 , and l_3 , u_3 respectively, as well as the frequencies: e (response with both Radiesse and Restylane), f (response with Radiesse but no response with Restylane), g (response with Restylane but no response with Radiesse) and h (no response with both Radiesse and Restylane) based on the following SAS code:

```
proc freq data=a;
  by treatment;
  tables response/binomial(wilson);
run;
```

Second, obtain the two-sided 95% CI for the difference between proportions using Newcombe's method based on the following formulas and SAS code:

Formulas:

$$L = \hat{\theta} - \delta, U = \hat{\theta} + \varepsilon$$

where

$$\delta = \sqrt{dl_2^2 - 2\hat{\phi}dl_2du_3 + du_3^2}, \varepsilon = \sqrt{du_2^2 - 2\hat{\phi}du_2dl_3 + dl_3^2},$$
$$dl_2 = (e + f)/n - l_2, du_2 = u_2 - (e + f)/n,$$
$$dl_3 = (e + g)/n - l_3, du_3 = u_3 - (e + g)/n,$$
$$n = e + f + g + h,$$

and if $eh > fg$, $\hat{\phi} = \max(eh - fg - n/2, 0)$; if $eh \leq fg$,

$\hat{\phi} = (eh - fg)/\sqrt{[(e + f)(g + h)(e + g)(f + h)]}$, but $\hat{\phi} = 0$ if this denominator is 0.

SAS code:

```
n=e+f+g+h;
theta=e/ (e+f)-g/ (g+h) ;
d12=(e+f) /n-12;
du2=u2- (e+f) n;
d13=(e+g) /n-13;
du3=u3- (e+g) /n;
if e*h>f*g then phi=max (e*h-f*g-n/2,0) ;
else if (e+f) *(g+h) *(e+g) *(f+h)=0 then phi=0;
else phi=(e*h-f*g)/sqrt ((e+f) *(g+h) *(e+g) *(f+h));
delta=sqrt (d12**2-2*phi*d12*du3);
epsilon=sqrt (du2**2-2*phi*du2*du3+d13**2);
L=theta-delta;
U=theta+epsilon;
```

		Response with Restylane		
		yes	no	total
Response with Radiesse	yes	e	f	
	no	g	h	
	total			n

The confirmatory analysis will be based on the PPS using observed values only.

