8.4.2 Unblinding procedures

The blind for all personnel involved in this clinical investigation will not be broken until the Blind Data Review Meeting (BDRM) has convened, the Statistical Analysis Plan (SAP) has been finalized, and the database has been locked. The statistical analysis will proceed after the unblinding, which will be documented.

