4 DETERMINATION OF SAMPLE SIZE

The estimate of the sample size is based on the following assumptions:

- Estimate of treatment effects (i.e. proportion of responders) on Test (Radiesse) and Control (Restylane) sides are at least equal, i.e. $P_{test} \geq P_{control}$ (or $D = P_{test} - P_{control} \geq 0$).
- Non-inferiority margin, $\Delta = 10\%$ (i.e., maximum negligible difference between the test and control proportions).
- Type I error, $\alpha = 0.025$.
- Type II error $\beta = 0.2$ (i.e. statistical power, $1-\beta = 0.8$ or 80%).
- Proportion of pairs with discordant responses $\eta = 0.175$ (i.e. 17.5%).

Using the above assumptions for sample size calculation in nQuery yields 138 effectiveness evaluable subjects needed to carry out the non-inferiority hypothesis associated with the primary effectiveness endpoint. Accounting for a 20% attrition (attributable to dropout of subject and major protocol deviations), overall 20% more subjects will be enrolled resulting in a total of approximately 174 subjects that will be randomized into this trial.

Since this is a multi-center, competitive enrollment study, the target number of subjects to be enrolled per investigational site is 44. In order to ensure that adequate subjects are enrolled per investigational site for determination of treatment effect homogeneity (or lack thereof), a minimum of approximately 22 and maximum of approximately 66 subjects will be enrolled.

per investigational site. The specified proposed minimum and maximum number of subjects to be enrolled per investigational site minimizes the probability of any one site having a preponderance of treatment effect.

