Statistical analyses will be performed when all subjects reach the 6 Month post initial injection time point. Primary effectiveness variable, secondary effectiveness variables and AE data will be analyzed using the snapshot of data for the first 6 months. A Statistical and a Clinical Study Report will be generated for the aforementioned analysis. They will be amended by a description and discussion of the analyses performed when all subjects have completed the study. For further details on which tables are produced for the Clinical Study Report and which for the amendment, please refer to the TFLs.

No examination for early termination is planned.

7.4.3 *Data Monitoring Committee*

There will be no data monitoring committee for this study.

7.4.4 *Multiple Comparisons/Multiplicity*

Only the analysis of the primary effectiveness endpoint based on PPS using observed values is of confirmatory nature. Further analyses on the primary effectiveness endpoint are performed for sensitivity reasons. Analyses of all other endpoints/variables is of exploratory nature.

7.4.5 *Examination of Subgroups*

No subgroup examination will be performed for this study.

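### SAP 7.1.1: phi lacks its denominator in formula and code, so the primary lower limit usually cannot be computed; the coded theta is also not the difference in response proportions

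*SAP*

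**What the plan says.** SAP 7.1.1 sets the estimand and the decision rule. D "is defined as the difference between the proportion of responders on the side treated with Radiesse" and the corresponding proportion on the Restylane side. H0 "will be rejected if the lower bound of the 2-sided 95% CI lies above the non-inferiority margin" of −10%. The interval is to be Newcombe's method 10 for paired proportions, as in Protocol 12.4.2.1.

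The SAP then prints formulas and SAS code, with e = both sides respond, f = Radiesse only, g = Restylane only and h = neither. When eh > fg, both formula and code set phi to max(eh − fg − n/2, 0); the code reads "if e*h>f*g then phi=max (e*h-f*g-n/2,0"). When eh ≤ fg, both divide by sqrt[(e+f)(g+h)(e+g)(f+h)]. The code sets theta to e/(e+f) − g/(g+h). The formula list uses theta-hat without giving an expression for it.

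SAP 7.4.4 states: "Only the analysis of the primary effectiveness endpoint based on PPS using observed values is of confirmatory nature". SAP 2 says the plan is meant to guide the statistical programming.

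**The concern.** Phi enters delta and epsilon as a correlation, so it must lie between −1 and 1. Without the denominator it is a count that can run into the thousands, and the radicand of delta turns negative. The omission is identical in formula and code, so a reading fault in the PDF is unlikely.

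In the SAP's own 2×2 table (rows Radiesse, columns Restylane), e/(e+f) − g/(g+h) is the Restylane response rate among Radiesse responders minus that among Radiesse non-responders. That measures how strongly the two sides agree. It does not estimate D, which is (e+f)/n − (e+g)/n = (f − g)/n.

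Two further code lines differ from the printed formulas: delta lacks + du3², and epsilon uses du3 where the formula has dl3. The epsilon line affects only the upper limit, so it does not touch the non-inferiority decision.

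At stake is the only confirmatory test. As written it usually returns no lower limit. A programmer would notice that and repair phi, but the theta line runs without error and biases the result towards non-inferiority.

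**Working it through.** **Inputs (SAP 4 and 7.1.1).** Margin 0.10; alpha 0.025, applied as the lower limit of a two-sided 95% interval; power 80%; discordance η = 0.175; D = 0 for planning; 138 evaluable pairs. No response rate is given, so I assume control rates from 50% to 91.25%. The upper end is the ceiling 1 − η/2 that 17.5% discordance allows at D = 0.

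**The plan's own figure.** n = η(z0.975 + z0.80)²/Δ² = 0.175 × 7.849/0.01 = 137.4, rounded up to 138. This reproduces.

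**Which branch applies.** At D = 0 with response rate p on both sides, the expected proportions give eh − fg = (p − η/2)(1 − p − η/2) − (η/2)² = p(1 − p) − η/2. This is positive when p(1 − p) > 0.0875, that is p = [1 ± sqrt(1 − 0.35)]/2, or between 9.7% and 90.3%. The faulty branch is therefore the expected one.

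**Example: (e, f, g, h) = (85, 12, 12, 29).** Each side responds at 97/138 = 70.3%, so D = 0. The Wilson limits are 0.6220 and 0.7728, giving dl2 = 0.0809 and du3 = 0.0699.

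- eh − fg − n/2 = 2465 − 144 − 69 = 2252; the denominator is 97 × 41 = 3977.
- Correct: phi = 2252/3977 = 0.566. delta² = 0.006545 − 2(0.566)(0.0809)(0.0699) + 0.004887 = 0.00503, so delta = 0.0709 and the interval is −7.1% to +7.1%.
- Printed formula: phi = 2252. delta² = 0.0114 − 2(2252)(0.0809)(0.0699) = −25.5, so L is undefined. The code, without + du3², also gives −25.5.
- Coded theta, all else correct: 85/97 − 12/41 = +58.4%, so L = 58.4% − 7.1% = +51.3%.
- Phi and theta correct, coded delta: delta² = 0.006545 − 0.006405 = 0.00014, so L = −1.2%.
- Phi alone repaired: L = 58.4% − 1.2% = +57.2%.
- Coded epsilon, phi and theta correct: U = +7.7% instead of +7.1%.

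**A table where Radiesse is worse: (84, 4, 24, 26).** D = (4 − 24)/138 = −14.5% and the correct L is −21.7%, so non-inferiority is not met. With the coded theta (+47.5%) and all else correct, L = +40.3%.

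**Exact enumeration of the 2×2 tables at n = 138, discordance 17.5%:**

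| Control response | L undefined, phi as printed (D = 0) | False non-inferiority at D = −10%: coded theta, rest correct | False non-inferiority at D = −10%: phi and theta correct, coded delta |
|---|---|---|---|
| 50% | 100% | 100% | 0.05% |
| 65% | 100% | 100% | 1.8% |
| 70% | 100% | 100% | 5.6% |
| 75% | 100% | 100% | 12.2% |
| 80% | 100% | 100% | 15.0% |
| 85% | 99.4% | 100% | 10.9% |
| 90% | 40% | 99.97% | 6.3% |

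The correct method gives false non-inferiority of 2.4–3.1% and power of 77.6–80.0% over the assumed range. In the last column L is still undefined in 99.6%, 86%, 62%, 29%, 6%, 0.3% and 0% of trials, from top to bottom. With phi alone repaired, false non-inferiority is 38% at 70%, 71% at 75% and 94% at 80%.

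At the 91.25% ceiling with D = 0, the printed phi never makes L undefined. There the coded theta, with all else correct, gives 0.8% power instead of 77.8%.

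Simulation (5,000 tables per rate) agrees on the undefined share: 41% at 90% response with n = 138, and 42% with n = 174.

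**The case against.** The method is named correctly in both documents, D is defined in words, and SAP 7.1 asks for the difference of the paired proportions with its method 10 interval. A validated implementation would therefore give the right answer, and this is a transcription error rather than an open choice of analysis. That stands as mitigation. It does not cure the defect, because the SAP also prescribes a formula and code that contradict the named method.

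As written, the failure is a missing limit, not a false claim. For the literal code at D = −10%, false non-inferiority is 0.00% at 50–85% response and 0.26% at 90%. The high error rates arise only after partial repair. A lower limit of +51% beside a reported difference of 0 would also look wrong, since SAP 7.1 requires the proportions and the cross table. Both points are fair. They make detection likely, but after the data are seen.

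The code block is poorly reproduced in the text I worked from: the letter l appears as the digit 1, and the du2 line has no division sign. The delta and epsilon discrepancies could have the same origin, so the figures that rest on coded delta are conditional on that line being genuine. Phi, printed identically in both places, is not open to this doubt. Theta is a well-formed but different expression, so misreading is an unlikely cause.

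**Conclusion.** The concern holds. The phi error alone leaves the primary lower limit undefined in virtually every trial at response rates of 50–85% and in about 40% at 90%. This assumes 138 pairs, 17.5% discordance and D = 0; the response rates are an assumption. Only at the top of the feasible range does the limit usually exist. The coded theta does not estimate D at any response rate, and if left in place once phi and delta are repaired it would make the test meaningless. The delta discrepancy would also distort the error rate if the source file confirms it. The correction must be made before the test is run.

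**What to change.** In SAP 7.1.1, correct formula and code together:

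- phi = max(eh − fg − n/2, 0)/sqrt[(e+f)(g+h)(e+g)(f+h)] when eh > fg, and 0 if the denominator is 0;
- theta = (f − g)/n, also stated in the formula list;
- delta = sqrt(dl2² − 2·phi·dl2·du3 + du3²);
- epsilon = sqrt(du2² − 2·phi·du2·dl3 + dl3²).

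Check the coded theta, delta, epsilon and du2 lines against the source file. Validate the program on worked tables, including one with f = g, where theta must be 0 (for example 85, 12, 12, 29: −7.1% to +7.1%), and one where non-inferiority fails (84, 4, 24, 26: L = −21.7%).

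Do this before unblinding, which Protocol 8.4.2 already makes conditional on the point that "the Statistical Analysis Plan (SAP) has been finalized, and the database has been locked". The cost is a text and program correction; design, data collection and sample size are unaffected.

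### The SAS code for the primary lower confidence limit omits a squared term that the SAP's own formula contains, which makes the limit too high and raises the false non-inferiority rate

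*SAP*

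**What the plan says.** SAP section 7.1.1 says the interval for the paired difference will be "constructed using the Newcombe's recommended method¹ [Newcombe, 1998, method 10", the same method that protocol section 12.4.2.1 names. The null hypothesis "will be rejected if the lower bound of the 2-sided 95% CI lies above the non-inferiority margin" of -10%, the margin being described as "the clinically negligible difference, is 0.10 (or 10.0" percent). SAP section 4 sets "Type I error, $\alpha = 0.025".

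Section 7.1.1 then gives the lower limit twice:

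- **Formula.** Delta is the square root of dl2² - 2·phi·dl2·du3 + du3². The end of the radicand reads "2\hat{\phi}dl_2du_3 + du_3^2".
- **SAS code.** The corresponding line is "delta=sqrt (d122-2*phi*d12*du3", where the first term is dl2 squared and the bracket then closes. L is set to theta minus this delta.

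The next code line, for the upper limit, keeps its third squared term: "epsilon=sqrt (du22-2*phi*du2*du3+d132". The text presents the formulas and the code together as the way to obtain the interval and does not say which prevails if they differ.

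**The concern.** In this notation dl2 is the distance from the Radiesse proportion down to its Wilson lower limit, and du3 is the distance from the Restylane proportion up to its Wilson upper limit. Both belong in the lower limit of the difference. Without du3², the Restylane uncertainty enters only through the cross term, which is subtracted when phi is positive. Delta is then too small, or the radicand is negative and L is missing.

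Section 7.4.4 makes the per-protocol analysis of this endpoint the only confirmatory one, and L is the only number it uses. A limit that is too high turns failures into non-inferiority claims.

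The same block has two other errors. Phi lacks its denominator when eh > fg ("if e*h>f*g then phi=max (e*h-f*g-n/2,0"), and theta is coded as a difference of row-conditional proportions instead of (f - g)/n. Those sit on other lines. Correcting them leaves the delta line as it is, and it then returns plausible numbers.

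**Working it through.** **Inputs.** From SAP section 4: 138 evaluable pairs, discordance eta = 0.175, one-sided alpha 0.025, power 80%, margin 0.10. From section 7.1.1: the two versions of delta and the rule L > -0.10. Assumed, because the documents give no rate: Restylane success of 60% to 90%.

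**The plan's own figure.** n = (1.960 + 0.842)² × 0.175 / 0.10² = 7.849 × 17.5 = 137.4, rounded up to 138. This agrees with the SAP.

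**Corrections applied to both versions of L.** theta = (f - g)/n. When eh > fg, phi = max(eh - fg - n/2, 0) / sqrt[(e+f)(g+h)(e+g)(f+h)].

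**One table by hand.** Take e/f/g/h = 97/9/16/16, so n = 138.

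- theta = (9 - 16)/138 = -0.0507.
- Radiesse: 106/138 = 0.7681, Wilson lower limit 0.6910, so dl2 = 0.0771.
- Restylane: 113/138 = 0.8188, Wilson upper limit 0.8742, so du3 = 0.0553.
- phi = (1552 - 144 - 69)/sqrt(106 × 32 × 113 × 25) = 1339/3095.5 = 0.4326.
- dl2² = 0.00594; 2·phi·dl2·du3 = 0.00369; du3² = 0.00306.
- Printed formula: delta = sqrt(0.00594 - 0.00369 + 0.00306) = sqrt(0.00531) = 0.0729, so L = -12.4%. Non-inferiority is not shown.
- SAS line: delta = sqrt(0.00594 - 0.00369) = sqrt(0.00225) = 0.0475, so L = -9.8%. Non-inferiority is claimed.

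Two more tables: 95/9/15/19 gives -11.5% by the formula and -8.4% as coded, again reversing the conclusion. 98/12/12/16 gives -7.2% and -4.2%.

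**Direction.** The omitted term is a square, so removing it cannot enlarge delta. Over all 2x2 tables with n = 138, the coded L is never below the full L where it exists.

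**Error rate.** All tables with n = 138 were enumerated under the multinomial at the margin: D = -0.10 and eta = 0.175, so P(f) = (0.175 - 0.10)/2 = 0.0375 and P(g) = (0.175 + 0.10)/2 = 0.1375. A missing L counts as no claim.

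| Restylane success (assumed) | False claim, printed delta | False claim, coded delta | Coded L undefined |
|---|---|---|---|
| 60% | 3.1% | 0.5% | 95.7% |
| 70% | 3.1% | 5.6% | 62.4% |
| 75% | 3.0% | 12.2% | 29.0% |
| 80% | 2.7% | 15.0% | 5.9% |
| 85% | 2.6% | 10.9% | 0.3% |
| 90% | 2.5% | 6.3% | 0.0% |

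**Sensitivity, 75% to 85% success.**

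- By discordance (n = 138), the coded rate is 3.1-13.0% at eta = 13.75%, 9.2-16.1% at 20%, 7.1-14.3% at 25% and 6.1-10.7% at 30%.
- By number of pairs (eta = 17.5%), it is 10.6-14.6% with 120 pairs and 11.5-16.1% with 174.
- If a negative radicand were set to zero instead of missing, the rates at n = 138 and eta = 17.5% would be 32.7%, 20.2% and 11.2% at 75%, 80% and 85%.

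**After the fix.** With du3² restored, the error is 2.6-3.0% and the power at D = 0 is about 78-79% over 75-85% success, in line with the planned 80%.

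**Neighbouring lines.** The epsilon line multiplies du2 by du3 where the formula has dl3; this affects only the upper limit. The du2 line has no division sign. Read literally, that is a syntax error that would stop the step.

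**The case against.** The strongest reply is that the false-claim rates do not describe the code as it stands. They describe a block in which phi and theta have been repaired and delta has not. Run as written, the unscaled phi makes the radicand negative in essentially every trial at 60-85% success, and the du2 line would not run. A programmer would notice. Phi is also incomplete in the printed formula, so repairing it means going to the named method, where the whole interval would probably be checked. Delta itself is printed correctly just above the code.

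This is fair as to likelihood: the rates are conditional on a partial repair, and a programmer who follows the printed delta with a properly scaled phi avoids the error. It does not remove the contradiction. SAP section 2 says the plan should be precise enough to guide programming, and nothing ranks formula above code.

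The size also depends on assumptions. Restylane success of 75-85% is not in the documents. At 60% success, or at 75% success with 13.75% discordance, the false-claim rate is not inflated, because most trials then have no computable limit (96% and 68%).

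The missing term could in principle be a loss in reading the PDF. That is unlikely: the line is syntactically complete and the next one keeps its third term. The single missing slash in du2 is a more plausible reading loss, so that item is uncertain. The characters 12 and 13 in place of l2 and l3 were treated as reading artefacts.

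**Conclusion.** The concern holds. The SAP contradicts itself on the one limit that decides the confirmatory test, and the coded version errs in favour of non-inferiority wherever it yields a number. With phi and theta corrected, at the plan's own 138 pairs and 17.5% discordance, the false-claim rate is about 11-15% at assumed Restylane success of 75-85% and 6.3% at 90%, against a planned 2.5%. Below about 75% success the main harm is a primary limit that often cannot be computed. These figures count an undefined limit as no claim. This must be corrected before the analysis is programmed for unblinded data.

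**What to change.** In the SAS code of SAP section 7.1.1:

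- `delta = sqrt(dl2**2 - 2*phi*dl2*du3 + du3**2)`
- `du2 = u2 - (e+f)/n`, after checking whether the slash is already in the source file
- `epsilon = sqrt(du2**2 - 2*phi*du2*dl3 + dl3**2)`

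Make these together with the phi and theta corrections, since no one of them alone gives a correct interval. State that the named method and the printed delta and epsilon govern if code and text differ. Before unblinding, check the program against a hand-worked 2x2 table; 97/9/16/16, with a correct lower limit of -12.4%, separates the two versions of delta.

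The cost is a SAP text and code correction before database lock. Design, sample size and conduct do not change.
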